8.1. Primary Efficacy Endpoint

The primary efficacy endpoint is the change from baseline to Week 12 in post-exercise peak LVOT gradient. Baseline is defined as the last non-missing measurement of post-exercise LVOT gradient prior to the first dose. Post-exercise peak LVOT gradient will be analyzed using a mixed-effect model with repeated measures (MMRM). All data available from baseline (Screening) to Week 16 (EOS) will be included and missing data will be accounted for by the MMRM model. The model will include the fixed categorical effects of timepoint: baseline, Week 4, Week 12 (end of treatment), and Week 16 (EOS). An unstructured covariance structure will be assumed unless model diagnostics suggest otherwise.

This model will provide least-squares (LS) mean estimates with their corresponding standard errors at each time point. Comparison between baseline and Week 12 (end of treatment) will be based on the LS mean difference obtained from the MMRM, and will be presented with its associated two-sided 90% confidence interval. Statistical significance of the difference versus baseline will be evaluated at the two-sided 0.10 level. The primary efficacy endpoint will also be descriptively summarized by each timepoint.

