3 STUDY OBJECTIVES

3.1 Primary Objective

The primary objective of this study is:

- To characterize the effect of 12 weeks of MYK-461 treatment on reducing post-exercise peak LVOT gradient in subjects with symptomatic HCM and LVOT obstruction

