11.3 Statistical Analysis

Before database lock, a final statistical analysis plan (SAP) for clinical data and PK analyses will be prepared that will contain full details of all planned analyses. The analyses presented here represent an outline of the intended methodology.

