11.3.5.1 Primary Efficacy Endpoint

The primary efficacy endpoint is the change from baseline to Week 12 in post-exercise peak LVOT gradient.

Post-exercise peak LVOT gradient will be analyzed using a mixed-effect model with repeated measures (MMRM). All data available from baseline (Screening) to Week 16 (EOS) will be included and missing data will be accounted for by the MMRM model. The model will include the fixed categorical effects of timepoint: baseline, Week 4, Week 12 (end of treatment), and Week 16 (EOS).

This model will provide least-squares (LS) mean estimates with their corresponding standard errors at each time point. Comparison between baseline and Week 12 (end of treatment) will be based on the LS mean difference obtained from the MMRM, and will be presented with its associated 95% confidence interval. Statistical significance of the difference versus baseline will be evaluated at the 1-sided 0.05 level.

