3.4. Dose Adjustment/Modifications

All subjects in Part A will be assigned to a starting dose of oral MYK-461 based on body weight for doses ≥ 10 mg, which they will receive QD for 4 weeks. Subjects in Part B will be assigned a starting dose of 2 mg. At the Week 4 visit, dose adjustment may be performed based on the predetermined criteria in Section 3.1, Table 1 (Part A) and Table 2 (Part B). The subject will subsequently receive that dose from Week 5 (Day 29) through Week 12.

Subjects with abnormal hepatic laboratory values (e.g., alkaline phosphatase [ALP], aspartate aminotransferase [AST], alanine aminotransferase [ALT], total bilirubin [TBL], or international normalized ratio) or signs/symptoms of hepatitis may meet the criteria for withholding of study medication or other protocol-required therapies. Withholding is either permanent or conditional depending on the clinical circumstances discussed in the protocol.

4. General Statistical Considerations

All statistical analyses and programming of tables, figures, and listings will be performed by PPD using the SAS® Version 9.2 or higher (SAS Institute Inc., Cary, North Carolina, USA).

Unless otherwise specified, all tables will be presented with the columns labeled with the combination of 'initial dose'/'adjusted dose'.

Descriptive summaries will consist of the number and percentage of subjects in each category for discrete variables, and the sample size, mean, median, standard deviation (STDEV), first and third quartiles, minimum and maximum for continuous variables. For the analysis of primary endpoint using a mixed-effect model with repeated measures (MMRM), LS mean with standard error (SE) will also be provided. Standard error formatting should be presented to 4 more decimal places than the measured value.

P-values will be rounded to 4 decimal places. P-values that round to 0.0000 will be presented as '< 0.0001' and p-values that round to 1.000 will be presented as '> 0.9999'. Confidence intervals (CIs) will be estimated based on the MMRM for the analysis of the primary endpoint, a two-sided 90% significance level.

All mean and quartile values will be formatted to one more decimal place than the measured value. Standard deviation values will be formatted to 2 more decimal places than the measured value. All percentages will be rounded to 1 decimal point. The number and percentage of responses will be presented in the form XX (XX.X), where the percentage is in the parentheses.

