Plasma concentration data of MYK-461 will be listed by subject and summarized by MYK-461 dose level and nominal time point using descriptive statistics (number of subjects (n), arithmetic mean, standard deviation (SD), coefficient of variation (CV%), geometric mean, geometric CV%, median, minimum, and maximum).

Arithmetic mean plasma concentration data of MYK-461 versus nominal time (days) will be plotted by MYK-461 dose level on linear and semi-logarithmic scales. Individual plasma concentration data of MYK-461 versus actual times will also be presented on linear and semi-logarithmic scales. Overlay plot of individual plasma concentration data of MYK-461 versus actual times will also be presented on linear and semi-logarithmic scales.

11. PK-QTc Analyses

A concentration-QTc regression analysis, based on data collected from the ECG recordings after drug administration and MYK-461 concentration values for each subject at each matching timepoint will be performed. A linear mixed effects (LME) model will be fitted on change from

baseline QTcF, with baseline QTcF, MYK-461 concentration as an independent variable and subject as a random effect. Baseline QTcF is defined as the average of the last assessment prior to start of study treatment. A corresponding scatter plot will be provided. The analyses will be performed on PK/ECG set.

12. Pharmacogenomic/HCM Genotype

For all subjects who provide consent, blood will be drawn on prior to dosing Day 1 for assessment of HCM genotype and potentially additional deoxyribonucleic acid (DNA) sequencing.

In addition, subjects may consent separately to collection of pharmacogenetic samples that will be stored for potential future analysis of genetic biomarkers of efficacy, safety-related, PD, or PK parameters as determined by future studies using clinically meaningful endpoints, through DNA sequencing or other genetic testing.

Data collected for Pharmacogenomic and HCM Genotype will be listed and summarized as requested by the sponsor.

13. Interim Analysis

There will be an interim analysis for Part A subjects, when the last subject for Part A completes the study. The Part A interim analysis will include: demographics, disposition, adverse events, drug exposure, vital signs, laboratory evaluations, ECG, PK, primary and secondary efficacy endpoints.

14. Changes in the Planned Analysis

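### Does the SAP's two-sided 90% interval and 0.10 test, in place of the protocol's 95% interval and 1-sided 0.05 test, weaken the primary result?

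*SAP*

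**What the plan says.** Both documents take the primary comparison from the same MMRM, as the LS mean difference between baseline and Week 12. They differ in how it is reported and tested.

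- **Protocol 11.3.5.1** (and the synopsis): the difference "will be presented with its associated 95% confidence interval", and "Statistical significance of the difference versus baseline will be evaluated at the 1-sided 0.05 level". The sidedness of the 95% interval is not stated. Protocol 11.3.2 also makes 95% the general level for intervals, where appropriate.
- **SAP 8.1**: the difference is "presented with its associated two-sided 90% confidence interval", and "Statistical significance of the difference versus baseline will be evaluated at the two-sided 0.10 level".
- **SAP Section 4** (General Statistical Considerations) repeats the 90% figure for the primary endpoint but calls it "a two-sided 90% significance level".
- **SAP 4.1** still gives the sample size at 1-sided 0.05.
- **SAP Section 14**, headed "14. Changes in the Planned Analysis", has no text before the reference list.

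On the standing of its own analysis section, protocol 11.3 says: "The analyses presented here represent an outline of the intended methodology". It leaves the full details to the SAP.

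**The concern.** The SAP repeats most of the protocol's primary-analysis paragraph, so a different interval level and a different test level stand out as a substitution. Moving from 95% to 90% and from 0.05 to 0.10 reads like a relaxed standard. The section meant for such changes is empty.

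This is a single-arm pilot with about 10 subjects in each Part, and the Parts are analysed separately. The primary objective is "To characterize the effect of 12 weeks of MYK-461 treatment on reducing post-exercise peak LVOT gradient", so the estimate and its interval are the main result. If the change had raised the chance of a false claim of benefit, or if readers took a 90% interval for a 95% one, that result would look stronger than the data allow. The two-sided rule also permits an increase in gradient to be called significant, although the objective is framed around a reduction.

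**Working it through.** **Inputs.** n = 10 per Part, SD 35 mm Hg, 1-sided alpha 0.05 (protocol 11.1, repeated in SAP 4.1). Assumptions: the SD is that of the within-subject change, all 10 subjects are complete, and df = n − 1 = 9. Neither document names a degrees-of-freedom method for the MMRM, so other values are tried below.

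**Step 1: reproduce the plan's power.** SE = 35/√10 = 11.07 mm Hg. The noncentrality is δ/SE, for example 30/11.07 = 2.71. Power is the probability that a noncentral t with 9 df exceeds t(0.95, 9) = 1.833.

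| δ (mm Hg) | Plan's table | 1-sided 0.05 | 1-sided 0.025 | Difference (points) |
|---|---|---|---|---|
| 50 | > 99% | 99.4% | 97.9% | 1.5 |
| 40 | 95% | 95.4% | 89.4% | 5.9 |
| 30 | 80% | 80.3% | 67.5% | 12.8 |
| 20 | 50% | 51.0% | 36.5% | 14.5 |

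The plan's figures are reproduced at 1-sided 0.05. Differences come from unrounded values.

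**Step 2: compare the two tests.** A two-sided 0.10 test puts 0.05 in each tail, so its critical value for a reduction is again t(0.95, 9) = 1.833. Power and type I error for a reduction are therefore those of the 1-sided 0.05 test. What is added is the opposite tail: a 5% chance of declaring an increase when there is no change, and about 0.0015% when the true reduction is 30 mm Hg.

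**Step 3: compare the two intervals** (95% read as two-sided).

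- 90%: 1.833 × 11.07 = 20.3 mm Hg half-width.
- 95%: 2.262 × 11.07 = 25.0 mm Hg half-width.
- Ratio: 1.833/2.262 = 0.810, so the 90% interval is 19% narrower.

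With other degrees of freedom the ratio is 2.015/2.571 = 0.784 (22% narrower, df 5), 1.703/2.052 = 0.830 (17%, df 27) or 1.645/1.960 = 0.839 (16%, normal quantiles).

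**Step 4: which interval agrees with the test?** A two-sided 90% interval lies wholly on the reduction side of zero exactly when the 1-sided 0.05 test is significant. A two-sided 95% interval matches a 1-sided 0.025 test instead. Under the protocol's pairing, the test can be significant while the interval includes zero. The last column of the table gives how often: 12.8% of trials at a true 30 mm Hg reduction and 14.5% at 20 mm Hg. The SAP's pairing removes that conflict.

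**The case for a change.** The best case for acting is about the record. The SAP sets aside an interval level that the protocol states for the primary endpoint and again as a general rule, it has a section for such departures, and that section is blank. Aligning the interval with the 1-sided test is a plausible motive and would take one sentence to state, but the text reviewed does not state it. SAP Section 4 also ties the 90% level to the primary endpoint only, so the level for the other MMRM endpoints is left to inference.

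Much of this stands as a remark on documentation. The change is not recorded in the text reviewed, although the SAP's opening pages were not part of that text and could hold a version history. The term in SAP Section 4 should be confidence level. Neither point alters a result. The SAP gives 90% for the primary contrast in both Section 4 and 8.1, so an analyst knows what to compute. For the other endpoints, an analyst can choose a level and label it.

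Going back to 95% is a reporting preference. It would bring back the mismatch shown in Step 4 and would then need a note to explain it. A reader who wants the 95% interval can approximate it from the LS mean difference and the 90% limits once the degrees of freedom are known or assumed.

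The added upper tail does no harm. The objective is to characterize an effect, and being able to report an increase does not make a claimed reduction easier.

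**Conclusion.** No change to the plan follows. The two documents do differ, but the estimate, its standard error, and the critical value, power and 0.05 error rate for a reduction are the same under both. The visible effect is an interval about 19% narrower (16% to 22% over the degrees of freedom tried), labelled as 90% and consistent with the 1-sided 0.05 basis on which the study was sized. The protocol leaves the detail to the SAP. What is left is a missing log entry and a clerical slip in one term.

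The figures rest on 10 complete subjects per Part, a within-subject SD of change of 35 mm Hg, and the protocol's 95% interval being two-sided. If a one-sided 95% bound was meant, its limit coincides with the corresponding limit of the SAP's 90% interval, and the discrepancy is smaller still.

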8.2. Secondary and Exploratory Efficacy Endpoint

The proportion of subjects achieving LVOT gradient responses of < 30 mm Hg and < 10 mm Hg will be summarized at each post-baseline visit as well as across all post-baseline visits. In case of missing data at a given visit, it will be assumed that the subject had not achieved an LVOT gradient response.

Figures presenting mean +/- SE of resting, post-exercise and provoked LVOT gradient by timepoint will be included in the analyses.

Quantitative endpoints, including the Dyspnea numeric rating scale (NRS), pVO₂, VE/CO₂, LVEF, NYHA functional classification, NT-proBNP, and KCCQ OSS will be analyzed using the same MMRM model as for the primary efficacy endpoint. The list of timepoints included in the MMRM will be adjusted according to the visits at which each endpoint will be measured. All efficacy endpoint will also be descriptively summarized by each timepoint.

Change from baseline in heart rate and heart rhythm using a cardiac monitoring skin patch will be analyzed descriptively. Resting echocardiogram (ECHO) and hemodynamic stress echocardiography (HSE) parameters will be presented in a listing.

9. Safety Analysis

All safety analyses will be performed on the Safety Analysis population.

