1.2.1 MYK-461-002

In Study MYK-461-002, single doses from 1 mg to 48 mg were administered as an oral suspension to healthy men. All dose levels were well tolerated, with no serious adverse events (SAEs), deaths, or withdrawals from study due to adverse events (AEs) reported. The incidence of treatment-emergent AEs did not appear to increase with dose. The pharmacokinetic (PK) profile of MYK-461 displayed rapid absorption and subsequent distribution followed by a long elimination phase, with a mean elimination half-life of approximately 8 days. Single doses of ≥ 12 mg of MYK-461 were associated with detectable reductions in LV contractility from baseline as assessed by 3 independent echocardiographic measures (left ventricular ejection fraction [LVEF], LV fractional shortening (LVFS), and LVOT velocity time integral [VTI]). At the highest dose studied in healthy subjects (48 mg), mean reduction in LVEF at any timepoint was -6% relative to baseline. No changes in systolic blood pressure (BP) or heart rate (HR) were detected at any of the dose levels tested in this study.

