3.2 Secondary Objectives

The secondary objectives of this study are:

- To assess the proportion of subjects achieving an LVOT gradient response of post-exercise peak gradient < 30 mm Hg in subjects with symptomatic HCM and LVOT obstruction
- To assess the effects of 12 weeks of MYK-461 treatment on dyspnea symptom score, peak oxygen uptake (pVO_2), and volume expired (VE)/carbon dioxide production (VCO_2) slope in subjects with symptomatic HCM and LVOT obstruction
- To evaluate the PK of MYK-461 in subjects with symptomatic HCM and LVOT obstruction
- To evaluate the PD of MYK-461 in subjects with symptomatic HCM and LVOT obstruction as assessed by a variety of echocardiographic imaging parameters in subjects with symptomatic HCM and LVOT obstruction
- To evaluate the safety and tolerability of MYK-461 in subjects with symptomatic HCM and LVOT obstruction
- To evaluate the posttreatment reversibility of the effects of MYK-461 after 4 weeks of washout in subjects with symptomatic HCM and LVOT obstruction

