5.5 Withdrawal and Replacement of Subjects

5.5.1 *Withdrawal from the Study*

Study participants may withdraw from further participation in the study at any time and for any reason. The degree to which a study participant withdraws can vary, and efforts will be made to collect important safety data if feasible and the study participant agrees. Study participants can:

- Withdraw from treatment and agree to participate in the Early Termination and End of Study (EOS) visits
- Withdraw from treatment and agree to participate in the Early Termination visit
- Withdraw from treatment and all follow-up

The investigator or MyoKardia may withdraw a study participant from treatment in the study for any of the following (or other) reasons:

- AE
- Noncompliance with study procedures/restrictions
- Study termination by MyoKardia

In all cases, the reason(s) for study withdrawal will be recorded in the source document and on the appropriate electronic case report form (eCRF).

5.5.2 *Replacement of Subjects*

Subjects who do not receive MYK-461 may be replaced. Subjects who drop out of the study for reasons other than AEs after receiving study medication may be replaced at the discretion of MyoKardia.

All data from subjects who receive at least 1 dose of IMP will be documented and maintained in the clinical trial database.

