3.1. Overall Study Design and Plan

This is a non-randomized, phase 2 open-label pilot study to evaluate the efficacy, PK, PD, safety, and tolerability of MYK-461 in subjects with symptomatic HCM and LVOT obstruction. Approximately 20 adult subjects with symptomatic HCM, a resting LVOT gradient ≥ 30 mm Hg, and post-exercise peak LVOT gradient ≥ 50 mm Hg will be enrolled. Approximately 10 subjects will participate in Part A and approximately 10 subjects will participate in Part B. The study will have a 12-week treatment phase and a 4-week washout phase (Figure 1).

Figure 1 Study Schema

CPET, cardiopulmonary exercise training; D, day; HSE, hemodynamic stress echocardiography; N, number PK, pharmacokinetic sample; RE/V, resting echocardiography/Valsalva; W, week

At Screening, subjects will undergo transthoracic echocardiography (TTE) in the supine or left lateral decubitus position. In addition to a standardized complete TTE, both resting instantaneous peak LVOT gradient (baseline) and provoked peak LVOT gradient (Valsalva maneuver) will be collected. Subjects will then undergo a standard symptom-limited exercise test (hemodynamic stress echocardiography). Subjects will be assessed systematically for symptoms of dyspnea and/or angina. Instantaneous peak LVOT gradient will be assessed immediately post-exercise by TTE.

On Day 1, resting TTE will be performed, blood samples will be drawn for PK, and subjects will have an assessment of pVO₂, VE/VCO₂, and other variables via cardiopulmonary exercise testing (CPET). After CPET, subjects will be dosed with open-label oral MYK-461 at the investigational site and will be observed for at least 1 hour after dosing, with assessment of vital signs and electrocardiograms (ECGs) at 1 hour postdose. Subjects will then be supplied with MYK-461 sufficient for once daily (QD) dosing at home.

Subjects will be evaluated at the investigational site at Weeks 1, 2, 3, 4, 5, 6, 7, 8, 12, and 16. At each of these visits, resting TTE will be performed and blood samples will be drawn for PK. On study visit days, study medication will be administered at the investigational site in order to collect blood samples for PK ≤ 2 hours prior to dosing. At Weeks 4, 12, and 16, hemodynamic stress echocardiography will be performed and peak LVOT gradient will be assessed. CPET will be conducted between Weeks 10 and 12 (inclusive).

Part A:

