3.2.2 Secondary Endpoints

- Proportion of subjects achieving an LVOT gradient response of post-exercise peak gradient < 30 mm Hg
- Change in dyspnea symptom score from baseline to Week 12
- Change in pVO₂ and VE/VCO₂ from baseline to Week 12
- Change from baseline in LVEF 2-dimensional (2D) and 3-dimensional (3D), global longitudinal strain, and left ventricular fractional shortening (LVFS) from baseline to Week 12
- Change from Week 12 to Week 16 in post-exercise peak LVOT gradient
- Plasma PK profile of MYK-461 treatment

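### Counting a missing stress echo as non-response at the Week 16 washout visit can show loss of response that nobody measured, though only in the descriptive responder summaries

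*SAP*

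**What the plan says.** - **Rule.** SAP 8.2 states: "In case of missing data at a given visit, it will be assumed that the subject had not achieved an LVOT gradient response". Protocol 11.3.5.2 has the same rule. Neither makes an exception for any visit.
- **Visits covered.** In the SAP the below-30 (secondary) and below-10 mm Hg (exploratory) proportions "will be summarized at each post-baseline visit as well as across all post-baseline visits". The summary across visits is not in protocol 11.3.5.2, and the SAP does not define it.
- **When the gradient is measured.** SAP 3.1: "At Weeks 4, 12, and 16, hemodynamic stress echocardiography will be performed and peak LVOT gradient will be assessed". Week 16 is four weeks after the end of treatment.
- **Why Week 16 exists.** Protocol 3.2 lists as a secondary objective "To evaluate the posttreatment reversibility of the effects of MYK-461 after 4 weeks of washout".
- **Endpoint for that objective.** SAP 3.2.2 lists "Change from Week 12 to Week 16 in post-exercise peak LVOT gradient". This is a continuous measure. SAP 8.1 models the gradient by MMRM with Week 16 as a timepoint: "All data available from baseline (Screening) to Week 16 (EOS) will be included and missing data will be accounted for by the MMRM model".

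**The concern.** Counting missing as failure is a cautious choice while failure is the unfavourable outcome, as it is at Weeks 4 and 12. At Week 16 the question turns round. The drug has been stopped, the trial asks whether its effect has gone, and a subject no longer below the threshold supports reversibility. The same rule then fills a gap with the expected answer.

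A reader who sets the Week 12 responder rate beside the Week 16 rate will take the drop as evidence of reversal. Part of that drop may be subjects who had no echo. With about 10 subjects per part, one or two such subjects visibly change the table.

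**Working it through.** **Plan's own figures.** The documents give no expected response or dropout rate, so there is no planned responder figure to reproduce. The one computed figure, the power table in SAP 4.1, does reproduce. A one-sample t-test on the change (n = 10, SD 35 mm Hg, one-sided 0.05) gives 99.4%, 95.3%, 80.3% and 51.0% for 50, 40, 30 and 20 mm Hg, against the stated >99, 95, 80 and 50. It does not depend on the missing-data rule.

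**Formula.** Let N be the subjects in the part, T12 and T16 the true numbers of responders at each visit, and k12 and k16 the would-be responders whose echo is missing at that visit. Under the rule:

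- reported Week 12 rate = (T12 − k12)/N
- reported Week 16 rate = (T16 − k16)/N
- reported drop = true drop + (k16 − k12)/N

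With N = 10 (SAP 4.1), each subject in k16 adds 1/10 = 10 points of apparent reversal and each subject in k12 removes 10 points. SAP section 4 also splits tables into initial/adjusted dose columns; those hold fewer subjects, so the step there is larger.

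**Illustration (assumed counts).** Suppose 8 of 10 respond at Week 12, none truly reverses, and m of the 8 have no Week 16 echo. Week 12 is 80% throughout and the true drop is 0.

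| m | Week 16 under the rule | Apparent reversal | Week 16 observed n/N | Week 12 responders with both echoes, still responding | Bounds for Week 16 |
|---|---|---|---|---|---|
| 1 | 7/10 = 70% | 10 points | 7/9 = 78% | 7/7 | 70–80% |
| 2 | 6/10 = 60% | 20 points | 6/8 = 75% | 6/6 | 60–80% |
| 3 | 5/10 = 50% | 30 points | 5/7 = 71% | 5/5 | 50–80% |

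The observed rate alone does not return to 80% here, because only responders are missing. The paired count shows that no measured responder reversed. The lower bound is the figure that the SAP would report.

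**Cases without that effect.**

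- Missing at both visits: non-responder at both, so no change appears.
- Would-be responder missing only at Week 12: the Week 12 rate is too low and apparent reversal shrinks.
- Week 12 responder who misses Week 16 and truly reversed: classified correctly.

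**How Week 16 alone could be missing.** Protocol 5.5.1 lets a subject "Withdraw from treatment and agree to participate in the Early Termination visit" without the final visit. SAP section 4 assigns visits by study day, with Week 12 as Days 79–99. An Early Termination echo before Day 79 is outside that window, so Week 12 is missing as well and no drop appears. This route matters only if termination falls within Days 79–99, or if the combined Week 12/Early Termination visit label overrides the windows. The plainer route is a subject who completes Week 12 and does not return.

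**Summary across visits.** Its exposure depends on its meaning. If it means response at any visit, a Week 12 responder already counts and a missing Week 16 echo changes nothing. If it means response at every visit, the missing echo turns that subject into a failure.

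**The case against.** The strongest reply is that responder status is not the planned measure of reversibility. The only listed Week 12 to Week 16 endpoint is the continuous gradient change, and this imputation never enters its model. Neither document plans a comparison of responder rates between those visits. This stands, and it confines the problem to descriptive output. It does not remove the problem, because the Week 16 rate will still be tabulated under a rule chosen for efficacy.

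Second, non-response may simply be true. Protocol 1.2.1 reports single-dose data in healthy men "with a mean elimination half-life of approximately 8 days"; 28/8 = 3.5 half-lives leaves 0.5^3.5 = 8.8% of the drug. Entry also requires a post-exercise gradient of at least 50 mm Hg, above both thresholds. Non-response is therefore a plausible guess for a missing echo. But the washout visit is there to measure reversal, and filling a gap with the expected value adds no evidence.

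Third, much is already visible. SAP 8.1 summarises the gradient by timepoint, descriptive summaries carry the sample size, and stress echo results are listed by subject. A careful reader could recount the Week 16 responders. This lowers the stakes, but the table should not need recounting.

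A reader might infer that missing echoes always push towards full reversal, or that the trial's reversibility conclusion is unsafe. The documents support neither: the three cases in the working contradict the first, and the continuous endpoint answers the second.

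**Conclusion.** The point holds in a limited form and is minor. The rule covers Week 16, and there it can overstate loss of response by 10 percentage points for each Week 12 responder who has no Week 16 echo and would still have responded. That size assumes about 10 subjects per part, all kept in the denominator. How many such subjects to expect is unknown.

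The error sits in the below-30 and below-10 mm Hg summaries at Week 16 and possibly in the summary across visits. It should not be read as a flaw in the listed reversibility endpoint, nor as a bias that every early withdrawal produces.

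**What to change.** In SAP 8.2, apply missing-as-not-achieved at Weeks 4 and 12 only. For Week 16, report:

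- responders among subjects with a stress echo (n/N observed), with the number missing;
- the bounds with all missing counted as non-responders and all counted as responders;
- a Week 12 by Week 16 cross-tabulation of responder status for subjects with both echoes.

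State whether Week 16 enters the summary across visits. State also that the reversibility conclusion rests on the continuous Week 12 to Week 16 gradient change. SAP 8.1 describes only the baseline to Week 12 comparison, so that contrast should be written in.

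The cost is a few sentences in SAP 8.2 and extra rows in Tables 14.2.1.3.A and 14.2.1.3.B. The Week 16 denominator may then differ from that at Week 12. The observed rate also assumes that subjects who did not return resemble those who did, which is why the bounds belong beside it.
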